6 ETHICAL CONSIDERATIONS

The study will be carried out in accordance with the ethical principles that have their origin in the Declaration of Helsinki adopted by the 18th World Medical Assembly, Helsinki, Finland in 1964 and amended in Tokyo (1975), Venice (1983), Hong Kong (1989), South Africa (1996), Edinburgh (2000), Washington (2002), Tokyo (2004), Seoul (2008), Brazil (2013); and the Laws and Regulations in force in Europe and Spain, and with respect to the current legislation.

The rights, safety, and welfare of the study subjects take precedence over the study. The benefits obtained involve achieving an improvement in cognitive functions and getting a job.

Free informed consent will be obtained from each subject prior to their participation in the study. The procedure used to obtain it will be specified. The confidentiality of records that could identify subjects is protected by respecting privacy and confidentiality standards in accordance with relevant legislative requirements.

The patient must give her consent before being admitted to the clinical study. The doctor must explain the nature, purposes and possible consequences of the study, in a way that is understandable to the patient. The information provided by the doctor must also be recorded.

The subject of the study will grant their consent by signing the corresponding model that must also bear the signature of the researcher. In Annex II (page 16-18), a copy of the informed consent model is attached. The investigator will not initiate any research corresponding to the study without the patient's consent.

In order to guarantee the confidentiality of the data of the patients participating in the study, only the following individuals will be able to access this information: the researcher and their team of collaborators, the representative of the sponsor who will carry out the monitoring tasks, the auditor in the event that the study was submitted to an audit, the CEIm and the Health Authorities.

The treatment, communication and transfer of the personal data of all the participating subjects will comply with the provisions of Organic Law 3/2018, of December 5, on the Protection of Personal Data and guarantee of digital rights, and the application of the Regulation (EU) 2016/679 of the European Parliament and the Council of April 27, 2016 on Data Protection (RGPD).

ANNEX I

FLOWCHART

Suitability assessment (n=100)

Investigadores Colaboradores

Dr/Drs: [name]., [name], [name], [name], [name], [name], [name], [name], [name]

Research Partners

Your data and the collaborators' will be processed by the Canary Islands Health Service in compliance with the General Data Protection Regulation 2016/679. For the administrative and accounting management, if the funding for the study is approved, the data will be processed by the Canarian Foundation for Health Research (FUNCANIS), on a mandatory basis and without constituting a transfer of data, as a collaborating entity when executing administrative and accounting functions. These data will allow the Foundation to carry out the tasks of economic-administrative management of its research work, send you information related to it and to various procedures on reimbursements, payments, etc. On the other hand, it will allow the Foundation to carry out periodic research reports and relevant statistics. All this guaranteeing the security measures necessary for the treatment of information.

Study title: TRAINING IN COGNITION AND SOCIAL COMPETENCE IN PATIENTS WITH SCHIZOPHRENIA

Project summary:

A single-blind randomized clinical trial will be carried out in patients suffering from schizophrenia and who have the legal capacity to consent to the study. Study participants will be randomized to either the experimental group (e-Motional Training) plus Individual Placement and Support (IPS) or the control group (IPS alone).

The efficacy of a training program in cognition and social competence (e-Motional Training) will be evaluated in patients with schizophrenia when improving the recognition of basic emotions, social cognition, emotional intelligence and social competence.

INFORMATION ON THE USE OF RESOURCES AND FUNDING

(mandatory compliance)

Do you need funding for this study?				YES		NO	X
Do you have required funding for this study?				YES	X	NO	
How many hours of your time during work hours will you dedicate to this study?				25%			
Do you have the material means (equipment, techniques, others...?)				YES	X	NO	
Where will the study take place?							
CONSULTING ROOM	DAY HOSPITAL	UICEC	HOSPITALIZATION	X	OTHERS	SINPROMI	
Will additional tests be performed outside of routine clinical practice?*				YES		NO	X
*If YES, indicate below:							

Statistical analysis plan

Online Training Program on Social Cognition for Patients With Schizophrenia

NCT ID not yet assigned

ULaguna
18-12-2019

Study title: TRAINING IN COGNITION AND SOCIAL COMPETENCE IN PATIENTS WITH SCHIZOPHRENIA

A single-blind randomized clinical trial will be carried out in patients suffering from schizophrenia and who have the legal capacity to consent to the study. Study participants will be randomized to either the experimental group (e-Motional Training) plus Individual Placement and Support (IPS) or the control group (IPS alone).

For data analysis, taking into account that not all patients will have pre and post information, general mixed models will be used with identification of the subject and repeated time measurements (pre and post).

It will be carried out for the analysis of the mean tests as variance (t-student test of independent samples and Levene's test of equality of variances),

The efficacy of a training program in cognition and social competence (e-Motional Training) will be evaluated in patients with schizophrenia when improving the recognition of basic emotions, social cognition, emotional intelligence and social competence.

INFORMATION ON THE USE OF RESOURCES AND FUNDING

(mandatory compliance)

Do you need funding for this study?				YES		NO	X
Do you have required funding for this study?				YES	X	NO	
How many hours of your time during work hours will you dedicate to this study?				25%			
Do you have the material means (equipment, techniques, others...)?				YES	X	NO	
Where will the study take place?							
CONSULTING ROOM	DAY HOSPITAL		UICEC		HOSPITALIZATION	X	OTHERS SINPROMI
Will additional tests be performed outside of routine clinical practice?*				YES		NO	X
*If YES, indicate below:							
Use of biological samples:				YES		NO	X
*If YES, indicate their location below:							
SERVICE / DEPARTMENT: PSYCHIATRY SERVICE. ULL.							
COLLECTION				YES		NO	X
BIOBANK				YES		NO	X
Use of patient clinical data:							
Transfer of encrypted data (pseudonymized) outside the EU to the entities of our group, to service providers or to scientific researchers who collaborate with us				YES		NO	X

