 - Attributive style, understood as the tendency that individuals have to explain the events that happen to them in life and that often leads to considering negative events as caused by the bad intentions of others.

People with schizophrenia tend to isolate themselves, showing little initiative and motivation towards activities, especially social ones, than before the onset of the illness. They suffer from social isolation because they find it difficult to establish contact with other people and carry on a conversation, they have difficulty functioning normally under stressful conditions, in part due to their difficulties in social skills and problem solving.

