4 METHODS

4.1 DESIGN

A single-blind randomized clinical trial (Annex I) will be carried out in patients suffering from schizophrenia and who have the legal capacity to consent. Study participants will be randomized to either the experimental group (e-Motional Training) plus Individual Placement and Support (IPS) or the control group (IPS alone).

Sample size calculation:

Taking as a reference the results of the pilot study in schizophrenia carried out by the research team in Galicia ([name] et al), where the average reached in the group before the intervention in the Stories of Theory of Mind by F. Happé in his Spanish version by Pousa (1999) was 8.5 points with a standard deviation of 3.61 points and where, after the intervention, the mean score achieved was 11.67 and the standard deviation was 4.72, for a power of 80% and a confidence level of 95%, the necessary sample in each group would be 30 patients, assuming losses of 5%. An attempt will be made to obtain a total sample of 80 people, taking into account losses during follow-up.

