- *Mayer-Salovey-Caruso Emotional Intelligence Test (MSCEIT)*¹⁶: This allows an evaluation of general emotional intelligence based on the subject's performance. It is made up of 141 items and the duration of its completion varies between 30 and 45 minutes, approximately.
- *Movie for the Assessment of Social Cognition (MASC)*¹⁷: the Spanish version of Lahera (2014) will be used. In this test, the subject must understand the various interactions established between the four characters and is asked about them through 40 multiple-choice questions. Questions include jokes comprehension, double meanings, innuendos, easily expressed emotional reactions, nonverbal cues or blunders. The test gives a social cognition score, but it also allows classifying the predominant type of error (hypo-mentalization, or a tendency to infer less social meaning than there is, or hyper-mentalization, or a tendency to over attribution).
- *Positive and Negative Symptom Scale (PANSS)*¹⁸: It consists of 30 items that evaluate the schizophrenic syndrome from a dual perspective; a dimension that evaluates the severity of the positive syndrome, the negative syndrome and the general psychopathology of the schizophrenic disorder; and another category that classifies it as positive, negative or mixed.
- *Social Functioning Scale (SFS)*¹⁹: This is a reliable instrument, specifically designed for the evaluation of the social functioning of people with schizophrenia. It is useful for researchers and clinicians interested in the variables involved in social functioning and, particularly, for those who work in family interventions or other psychosocial intervention programs in schizophrenia. It is composed of seven subscales: isolation/social integration, interpersonal communication, independence-execution, interdependence-competence, free time, prosocial activities, employment/occupation.

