4.6 STATISTICAL ANALYSIS OF DATA

All data will be analyzed with the SPSS program.

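### The SAP's provision for missing pre/post scores makes no use of baseline PANSS, so symptom-related loss that differs by arm can bias the arm difference in favour of training

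*SAP*

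**What the plan says.** The SAP's data-analysis paragraph starts from the expectation of missing scores and gives one answer: "taking into account that not all patients will have pre and post information, general mixed models will be used with identification of the subject", together with time (pre, post). It does not name arm, arm-by-time, any covariate, a missing-data assumption or a sensitivity analysis. The only other method it names is "t-student test of independent samples and Levene's test of equality of variances".

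Protocol section 4.6 adds nothing on missing data: "All data will be analyzed with the SPSS program".

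PANSS is in the battery given before and after training (Protocol section 4.4: "It consists of 30 items that evaluate the schizophrenic syndrome from a dual perspective"). Protocol section 4.3 gives symptoms a role only as a secondary outcome. No text makes baseline PANSS a covariate or an auxiliary variable.

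On losses, Protocol section 4.1 states 30 per group with 5% loss, then adds: "An attempt will be made to obtain a total sample of 80 people, taking into account losses during follow-up".

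**The concern.** A likelihood-based pre/post model gives a valid arm difference when missingness depends only on what the model contains. As written, that is the observed score on the same test. If patients with worse symptoms are more often missing at the post assessment in one arm, and symptoms carry information about the post score that the pre score does not, the model leaves out a driver of the missingness.

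The protocol gives some reason to think of this. Its introduction says: "People with schizophrenia tend to isolate themselves, showing little initiative and motivation towards activities, especially social ones". Only the experimental arm has twelve training sessions on top of employment support (section 5). A patient's own request is a ground for withdrawal (section 4.2.3), and such requests could be symptom-related.

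If sicker patients are lost mainly from the training arm, those who remain there have a better prognosis and the training looks more effective than it is. The t-test on observed scores is more exposed, because it does not use the pre score of those who left.

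**Working it through.** **1. The plan's own figure.** Inputs from Protocol section 4.1: pre mean 8.5 (SD 3.61), post mean 11.67 (SD 4.72), 80% power, 95% confidence.
- Difference: 11.67 − 8.5 = 3.17.
- SD: √((3.61² + 4.72²)/2) = 4.20.
- n = 2 × (1.96 + 0.84)² × 4.20² / 3.17² ≈ 27.6, so 28 per arm. Then 28/0.95 = 29.5, so 30 per arm, as stated. (A one-sided test with SD 4.72 also gives 28, then 30; the protocol does not state sidedness.)
- Standard error at 30 per arm: 4.20 × √(2/30) = 1.08.

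**2. Loss rates.** Stated: 5%. Implied room: (80 − 60)/80 = 25%. The 25% is an inference from the target, not a forecast in the protocol.

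**3. Assumptions the documents do not supply.** S is standardised baseline PANSS (higher is worse).
- Correlation of S with the pre score: ρ = −0.3.
- Pre-post correlation: r = 0.5 to 0.7.
- Partial correlation of S with the post score given the pre score: −0.2 to −0.5.
- Odds of loss per SD of S: 2 to 4 in the training arm, 1 in the control arm.
- The model contains arm-by-time, as any arm comparison needs.

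**4. Formula.** With the post score missing for some, the model's post mean in an arm is the regression of post on pre among those observed, evaluated at the mean pre score. If loss depends on S, the bias in the arm difference is approximately

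4.72 × g × (m_T − m_C), with g = partial correlation × √((1 − r²)(1 − ρ²)),

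where m_T and m_C are the mean of S among patients with a post score in each arm. For a logistic loss model with overall loss d and loss probability p(S), m = −E[S·p(S)]/(1 − d). Numerical integration gives:

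| Loss | m, odds 2 | m, odds 4 |
|---|---|---|
| 5% | −0.034 | −0.061 |
| 25% | −0.160 | −0.265 |

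**5. Results, loss unrelated to S in controls (m_C = 0).**
- Mildest case (r 0.7, partial −0.2, odds 2): g = −0.2 × √(0.51 × 0.91) = −0.136. At 25% loss, 4.72 × 0.136 × 0.160 = 0.10. At 5%, 4.72 × 0.136 × 0.034 = 0.02.
- Harshest case (r 0.5, partial −0.5, odds 4): g = −0.5 × √(0.75 × 0.91) = −0.413. At 25% loss, 4.72 × 0.413 × 0.265 = 0.52. At 5%, 4.72 × 0.413 × 0.061 = 0.12.

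Simulation over the same ranges (40 per arm, no true effect, 4,000 replicates) gave 0.10 to 0.55 at 25% loss and 0.02 to 0.16 at 5%. I use the wider simulated ranges: 0.10/3.17 = 3%, 0.55/3.17 = 17%, 0.16/3.17 = 5%. The observed-score t-test gave 0.22 to 0.74 at 25% loss (7% to 23%).

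**6. When it vanishes.** If m_T = m_C, or if g = 0, the bias is zero. A large-sample simulation with a true effect of 3.17 agreed: about 0 when both arms lost patients alike (25%, odds 3), and about 0 when PANSS added nothing beyond the pre score, at 5%, 25% and 40% loss. With odds 4 in training and 2 in control, the harshest case falls to 4.72 × 0.413 × (0.265 − 0.160) = 0.20.

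**7. With baseline PANSS in the model.** Bias was within about 0.03 points of zero in every simulated scenario.

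**8. Effect on the test.** At the upper end, 0.55/1.08 = 0.51 standard errors. A nominal two-sided 5% test then rejects with probability P(Z > 1.45) + P(Z < −2.47) = 0.073 + 0.007 = 8%. Direct simulation of the harshest case gave 7% to 7.6% for the pre-score-adjusted model. The observed-score t-test reached about 9%.

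**The case against.** The strongest reply is that no text predicts the two conditions the bias needs: symptom-related loss that differs by arm, and a PANSS-post link beyond the pre score.
- The sentence on low motivation is background on the illness and does not concern dropout.
- Eligibility points the other way. Patients must want regular employment (section 4.2.1), and those unable to work are excluded (section 4.2.2).
- Controls have the same illness and the same assessments, so their loss may follow symptoms too.
- Missed training is not a withdrawal criterion, and both groups are assessed before and after. Stopping training therefore need not mean a missing post score.
- The only stated loss is 5%, where the bias is negligible. Even the worst case at 25% is about half a standard error.

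All of this stands, and it makes the point conditional and modest in size.

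A reader might also infer that the SAP excludes PANSS. It does not. The SAP does not list its fixed effects and does not even name arm, so PANSS is unspecified rather than ruled out.

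Finally, the near-zero bias after adding PANSS is partly built in, because the simulations let loss depend on baseline PANSS alone. That shows the remedy works for this mechanism, not for every mechanism.

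What the reply does not remove is that the model was chosen because scores will be missing. What it conditions on therefore decides whether that choice works, and a relevant baseline measure is already in hand.

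**Conclusion.** The point holds in conditional form. The SAP's one provision for missing scores, as written, does not use baseline PANSS, and the arm difference can be biased towards training. The size is about 0.1 to 0.55 Happé points at an assumed 25% loss, at most about 0.16 at the stated 5%, and about zero if loss is alike in both arms or PANSS adds nothing to the pre score. The figures rest on assumed correlations and odds, since the documents give none.

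A reader might go further and conclude that the bias will occur, and on every main outcome. The documents support neither. Nothing in them establishes arm-differential loss, and only the Happé stories have the means and SDs needed for a calculation; the PANSS-post link may be nil for other tests.

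The change is still worth making before the data are seen. It is nearly free, and choosing covariates after seeing who dropped out would invite selective analysis.

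**What to change.** In the SAP's data-analysis paragraph:
- Write each main-outcome model as arm, time and arm-by-time, with subject as the repeated unit, plus one baseline PANSS score named in advance and its interaction with time. The interaction is needed so that PANSS can inform the post score separately from the pre score. Alternatively, use multiple imputation by arm with that PANSS score as an auxiliary variable; this also keeps any patient whose baseline PANSS is missing.
- Include every randomised patient with at least one score, and take the arm difference from this model.
- Treat the t-test on observed scores as descriptive.
- Report missing scores by arm.

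Cost: one or two sentences, no new data, visits or patients, and one or two degrees of freedom per model. In simulation the standard error with PANSS ranged from about 1% higher to about 11% lower.

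Limit: this does not remove bias from symptom change after baseline or from unmeasured reasons for loss. A short sensitivity analysis for data not missing at random would show how far those could matter.

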4.3 MAIN AND SECONDARY VARIABLES

Main study variables: improvement in the recognition of basic emotions, social cognition, emotional intelligence and social competence.

Secondary variables: improvement in symptoms and work results.

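### The SAP does not name the arm contrast that decides efficacy; a common-baseline arm difference at post would fix it with the planned data and may add power

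*SAP*

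**What the plan says.** The analysis text is very short.

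- **SAP, model.** The SAP proposes that "general mixed models will be used with identification of the subject and repeated time measurements (pre and post"). Its reason is incomplete data: "taking into account that not all patients will have pre and post information".
- **SAP, t-test.** A second sentence reads "It will be carried out for the analysis of the mean tests as variance (t-student test of independent samples and Levene"'s test of equal variances, and then breaks off at a comma. It does not say whether baseline, post or change scores are compared, or for what purpose.
- **Protocol 4.6.** "All data will be analyzed with the SPSS program". Nothing else is given there.
- **Protocol 4.3.** "Main study variables: improvement in the recognition of basic emotions, social cognition, emotional intelligence and social competence".
- **Protocol 4.1, sample size.** After a pilot pre-intervention mean of 8.5 (SD 3.61), "the mean score achieved was 11.67 and the standard deviation was 4.72". From this, "the necessary sample in each group would be 30 patients, assuming losses of 5" per cent, and then "An attempt will be made to obtain a total sample of 80 people, taking into account losses during follow-up".
- **Protocol 5.** Social cognition is assessed in both arms before and after the programme, by a blinded investigator.

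No arm term, arm-by-time term, baseline covariate or baseline constraint appears in either document. No pre-post correlation is given.

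**The concern.** An SAP should fix the deciding comparison before data are seen. Here at least three comparisons fit the wording: the arm-by-time contrast from the mixed model, a t-test on post scores, and a baseline-adjusted arm difference at post. They use the same scores but differ in precision and can give different answers.

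The mixed model is probably the intended main analysis, because the SAP justifies it by missing values. Since Protocol 4.3 speaks of improvement, its plain reading is an arm-by-time contrast, that is, a difference in change. At stake are a choice left open until analysis and, on the plain reading, precision that the planned baseline scores could already supply.

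**Working it through.** **Inputs.** From Protocol 4.1: pre SD s0 = 3.61, post SD s1 = 4.72, difference 11.67 − 8.5 = 3.17, 5% losses, target 80. Assumed: 1:1 allocation, two-sided 5% level, bivariate normal scores, the same SDs in both arms, and r = 0.3, 0.5 or 0.7. The 3.17 is a within-group pilot change and serves here only as a common yardstick for comparing methods. Evaluable per arm: 40 × 0.95 = 38.

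**Step 1: the plan's own figure.** Pooled SD = √((3.61² + 4.72²)/2) = 4.20. Then n = 2 × (1.96 + 0.84)² × 4.20² / 3.17², which rounds up to 28 per arm, and 28/0.95 rounds up to 30. The stated 30 is reproduced by a two-sample comparison that uses no baseline information. It is not a unique match: SD 4.72 with a one-sided test, and a paired formula at r = 0, also give 30.

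**Step 2: variance per patient for each contrast.**
- Post score only: s1²
- Change (arm-by-time in complete data): s0² + s1² − 2·r·s0·s1
- Baseline-adjusted post: s1²(1 − r²)

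Change minus adjusted equals (s0 − r·s1)². This is never negative and is zero only at r = s0/s1 = 3.61/4.72 = 0.76. Post minus adjusted equals r²·s1², which is zero only at r = 0.

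With the pilot SDs at r = 0.3:
- Change: 13.03 + 22.28 − 10.22 = 25.09
- Adjusted: 22.28 × 0.91 = 20.27
- Ratio: 0.808

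The adjusted/change ratio at r = 0.3, 0.5 and 0.7 is 0.808, 0.914 and 0.992 with the pilot SDs. With SD 4.20 at both visits it is 0.650, 0.750 and 0.850.

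**Step 3: power at 38 per arm** (100,000 simulated trials per setting).

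| SDs | Contrast | r = 0.3 | r = 0.5 | r = 0.7 |
|---|---|---|---|---|
| 3.61 / 4.72 | Post t-test | 82.3% | 82.3% | 82.3% |
| 3.61 / 4.72 | Arm-by-time | 77.8% | 89.0% | 98.1% |
| 3.61 / 4.72 | Baseline-adjusted | 85.1% | 91.1% | 98.0% |
| 4.20 / 4.20 | Post t-test | 90.0% | 90.0% | 90.0% |
| 4.20 / 4.20 | Arm-by-time | 78.4% | 90.1% | 98.7% |
| 4.20 / 4.20 | Baseline-adjusted | 92.0% | 96.1% | 99.5% |

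Hand check, pilot SDs, r = 0.3: the standard error is √(2V/38), which is 1.149 for change and 1.033 for adjusted. Φ(3.17/SE − 1.96) gives 78.8% and 86.6%, slightly above the simulated t-based values, as expected. Type I error was 4.9% to 5.1% for every test.

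**Step 4: the same loss in patients.** Dividing 38 by the variance ratio, arm-by-time would need about 47, 42 and 38 per arm (pilot SDs) or 58, 51 and 45 (SD 4.20) to match the adjusted analysis at 38.

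**Step 5: with incomplete data.** Take 40 per arm, of whom 36 have both values, 2 pre only and 2 post only (pilot SDs). Generalised least squares standard errors at r = 0.3, 0.5 and 0.7 are:
- Common-baseline mixed model: 1.035, 0.944, 0.783
- Ordinary arm-by-time: 1.158, 0.993, 0.789
- Post t-test: 1.083

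The corresponding powers are 85.5/91.2/97.9%, 77.1/88.3/97.8% and 82.4%. The gain therefore survives within the planned mixed model, and patients with one value are kept.

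**Step 6: only if the t-test on post scores were a rival deciding test.** With the pilot SDs it and arm-by-time disagree in 15% to 17% of trials, and reporting whichever is significant gives 8% to 9% false positives. Bias in the t-test from loss confined to below-average baseline scorers in one arm is small at the planned 5%: 2 × 0.05 × 0.3989/0.95 × r × 4.72 = 0.06, 0.10 and 0.14 points.

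**The case against.** The strongest reply is that the SAP is not silent on baseline. A repeated-measures model with pre and post takes baseline in as an outcome, and with main variables framed as improvement, arm-by-time is the natural reading. That contrast is valid, and one sentence naming it would end the ambiguity; the rest is a matter of efficiency. This largely stands, and it narrows the gap to two things: which coefficient decides, and whether the arms share a baseline mean. Neither is stated.

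The gain may also be negligible. With the pilot SDs it is about 2 points at r = 0.5 and nil at r = 0.7. The 14-point figure needs equal SDs of 4.20 at both visits, which the pilot does not show, and reproducing 30 per group does not establish them. If the true arm difference were half of 3.17, the gain with the pilot SDs would be about 5, 3 and 0 points at r = 0.3, 0.5 and 0.7. All figures come from one instrument, the Happé stories, so their size cannot be carried over to the other main outcomes. These limits stand.

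Finally, the t-test sentence is incomplete and might describe a baseline comparison. That is fair, so Step 6 carries little weight and the conclusion does not depend on it.

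**Conclusion.** The point holds. The deciding arm contrast and the baseline constraint are missing from both documents, and that does not depend on any assumption. The plain arm-by-time reading is not wrong, but in large samples it is never more precise than the baseline-adjusted difference at post, and the two are equal only at r = 0.76 with the pilot SDs.

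The power gain over arm-by-time is conditional: at 38 per arm, 7 to 14 points at r = 0.3, 2 to 6 at r = 0.5, and nil to 1 at r = 0.7. The lower figure in each range uses the pilot SDs and the upper uses SD 4.20 at both visits. These figures rest on an assumed r, 1:1 allocation, a two-sided test and the 3.17-point yardstick. This should be fixed: the plan is incomplete rather than invalid, and the remedy costs almost nothing.

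**What to change.** For each main outcome measured at both visits, name one deciding analysis in the SAP:

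- a mixed model on all randomised patients with a pre or a post value;
- fixed effects for time and arm-by-time, with a common baseline mean across arms (no arm main effect);
- unstructured pre/post covariance;
- the arm difference at post, with its 95% CI, as the deciding estimate.

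Label as sensitivity analyses a complete-case ANCOVA of post on arm and baseline, and a t-test on post scores in Welch form without a preliminary Levene test. The essential part is naming the contrast. Naming ordinary arm-by-time would also remove the ambiguity, but without the possible gain.

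Employment results recorded only after the programme have no matching baseline and are outside this change. Which instrument is primary and how multiplicity is handled are separate points.

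Cost: a few lines of SAP text, using the planned pre and post assessments and SPSS, with no extra patients or visits.
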